This database will be supervised and coordinated by PD [name], Bürgerhospital Frankfurt/M. (Webmaster).

4.8. Identification of data to be collected in the case report files (CRF) that should be considered as data source.

Data will be collected in E-CRF, provided by >[name] Wissenschaft, Berlin< on study software "Castor".

4.9. Definition of what is considered to be the end of the study.

The study will be finished after the 3 year-follow up examination concerning neurodevelopmental disabilities, which will be conducted on the surviving children of the participating patients.

5. Selection and withdrawal of subjects

5.1. Inclusion criteria.

- Dichorionic diamnionic twin pregnancy with
- 16-28 weeks of gestation
- Minimal age of 18 years
- Informed consent signature

5.2. Exclusion criteria.

- Monochorionic twin pregnancy
- Major fetal abnormalities (requiring surgery or leading to infant death or severe handicap)
- Cerclage prior to randomisation
- Uterine malformation
- Placenta previa totalis
- Active vaginal bleeding at the moment of randomization
- Spontaneous rupture of membranes at the time of randomization
- Silicone allergy

- Current participation in other RCT
- Painful regular uterine contractions

5.3. Withdrawal criteria.

If a participant may voluntarily withdraw from treatment or if it is necessary to remove the pessary due to the conditions described before, the patients will be followed as usual until delivery (intention-to-treat analysis).

The death of one twin is not an exclusion criterion for the pessary placement.

The replacement of patients is not applicable in this trial.

5.4. Rescue treatment criteria.

If the cervical length decreases later on during the pregnancy, the management of the pregnancy in each centre will be the usual.

In case of secondary cervical shortening in the follow-up period pessary treatment may be offered as a rescue treatment up to 32+0 weeks of gestation.

Cervical cerclage or progesterone are generally not indicated in twin pregnancies.

6. Treatment of Subjects

6.1. Treatments to be administered.

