A descriptive analysis by preterm birth will be carried out calculating means and medians for quantitative variables and proportions with 95% confidence intervals for categorical variables. In general, statistical comparisons with the pessary arm and the control arms or other group comparisons for primary and secondary outcomes will be performed with stratified tests as well as comparisons in the gestation subgroups. Events will be analysed for each twin and for single children assuming appropriate random effect regression models. Further subgroup analyses regarding the cervical length will be performed (e.g. CL 15 to 25mm and below 15mm). All tests, see also examples in the synopsis, will be two-sided using a significance level of $\alpha=0.05$.

For the primary endpoint we expect to have a drop out rate of up to 25% due to the long follow-up time (3 years) of the study; but we do not expect to have lost data for the secondary endpoints because for these parameters the study has a short follow-up time till time to birth only.

An interim analysis shall be conducted on key safety parameters after birth of 300 twins: the following safety endpoints will be assessed by a one-sided test with $\alpha=1\%$

- on level of the neonates: rate of preterm birth, time to birth, birth weight, death, neonatal morbidity, harm of intervention
- and on the maternal level: rate of hospitalisation for threatened preterm labour < 32 weeks, rate of PRoM <32 weeks, rate of infection / inflammation, rate of physical or psychological intolerance to pessary, rate of SAR/SAE, death.

The trial will be terminated as negative if a disadvantage for the pessary-treatment can be found in one of these tests. To guarantee a high safety level the significance level is chosen more conservatively than in a Bonferroni correction.

All analysis will be carried out with SPSS® version 19.0 or later (IBM Company SPSS Inc. Headquarters, Chicago, Illinois, USA) and R version 3.2.3 or later (R Foundation for Statistical Computing, Vienna, Austria).

Primary Outcome	Statistical Test
Children`s Long-Term Survival without Neuro-developmental Disability (3-Years-follow up)	Cochran-Mantel-Haenszel-Test, using 3 strata according to WoG
Secondary Outcome	Statistical Test
Birth before 34 Weeks of Gestation	Cochran-Mantel-Haenszel-Test, Chi-Quadrat Test
Time to Birth	Cox-Regression
Birthweight	van Elteren Test, Wilcoxon-Mann-Whitney Test
Fetal / Neonatal Death	Cochran-Mantel-Haenszel-Test, Chi-Quadrat Test

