Neonatal Morbidity	Cochran-Mantel-Haenszel-Test, Chi-Quadrat Test
Need for Hospitalization (mother)	Cochran-Mantel-Haenszel-Test, Chi-Quadrat Test
Days of Hospitalization (mother)	van Elteren Test, Wilcoxon-Mann-Whitney Test
Maternal Adverse Events	Cochran-Mantel-Haenszel-Test, Chi-Quadrat Test
Pessary Intolerance	Cochran-Mantel-Haenszel-Test, Chi-Quadrat Test
Vaginal Infections	Cochran-Mantel-Haenszel-Test, Chi-Quadrat Test

9.2. Expected number of subjects to be included.

For sample size calculation, we account for the stratified design and assume three equally large gestation groups. For the pessary group, we assume a combined event rate of at least 8% for the primary outcome and for the comparison of the pessary group with the control group we assume an odds ratio of 2.29. This odds ratio correspond to the lower bound of a one-sided confidence interval for the event rate given in van't Hooft (ProTwin Trial¹²). To reach a power of at least 80%, we have to evaluate at least 500 patients, 250 in the pessary group and 250 in the control group. To account for a drop out rate of 25%, overall n=672 pregnant women will be recruited.

9.3. Criteria for termination of the trial.

A non-justified case of maternal death (temporary stop until complete evaluation of the case by an external committee).

9.4. Selection of subjects to be included in each analysis.

The analysis will include all the subjects that have been randomised.

10. Direct Access to Data Source

Direct access will be granted to the authorized monitor, host institution and the regulatory authorities to permit trial-related monitoring, audits and inspections.

11. Quality and Control Assurance

Main investigator and collaborators: In order to ensure the Quality of the data they will provide instructions and training to the sites involved in the trial; review the CRF data; and detail of any other steps taken to ensure quality of research.

The main investigator will sign the study protocol and the “investigator’s commitment; he will apply for the Ethics Committee and the Director’s approval; and he will review the final report of the study.

The collaborators will assess patient’s eligibility, they will inform the patients and ask for the informed consent; and they will be responsible of the CRF and obtaining and registering all data.

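### The interim rule stops the trial on any one of 12 one-sided tests at 1%, which is looser than Bonferroni, and a stop is labelled negative although the 3-year outcome is not tested

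*Combined protocol and SAP*

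**What the plan says.** The interim analysis is described in section 9.1 of the combined protocol and SAP. It takes place after the birth of 300 twins; whether this means pairs or children is not stated. Each endpoint is tested one-sided at 1%.

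- Six endpoints are neonatal: "on level of the neonates: rate of preterm birth, time to birth, birth weight, death, neonatal morbidity, harm of intervention".
- Six are maternal: "rate of hospitalisation for threatened preterm labour < 32 weeks, rate of PRoM <32 weeks, rate of infection / inflammation", followed by "rate of physical or psychological intolerance to pessary, rate of SAR/SAE, death".

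The decision rule is "The trial will be terminated as negative if a disadvantage for the pessary-treatment can be found in one of these tests". The choice of level is explained by the remark that "the significance level is chosen more conservatively than in a Bonferroni correction", introduced as a way to secure a high level of safety. No family-wise level, number of tests or false-stop probability is given.

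Three other places bear on the rule:

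- Section 9.1 times the primary evaluation at 3 years after the last enrolled woman has delivered. The primary outcome is not among the interim endpoints.
- Section 4.9 says "The study will be finished after the 3 year-follow up examination".
- Section 9.3, on criteria for terminating the trial, has one entry: "A non-justified case of maternal death (temporary stop until complete evaluation of the case by an external committee". It does not mention the interim rule.

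**The concern.** A statistician who reads that a level is more conservative than Bonferroni expects a smaller per-test level and a family-wise false-positive rate below the nominal one. The 1% level gives the opposite for 12 tests. A committee or sponsor relying on the sentence would underestimate how often a harmless device ends the trial.

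The second problem is the conclusion attached to a stop. The trial asks about child survival without neurodevelopmental disability at 3 years. An excess of, say, maternal infection or hospitalisation is a reason to stop recruiting, but it says nothing about that outcome. Calling the trial negative at that point states a result that the data cannot support. The rule also does not say what happens to the 3-year follow-up of children already enrolled, and those data would be needed to weigh the harm against any benefit.

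**Working it through.** **Inputs from section 9.1.** Per-test level 0.01, one-sided; 6 + 6 = 12 endpoints; any one rejection stops the trial. Twelve is a minimum: section 4.1.2 gives five cut-offs for preterm birth and several components of neonatal morbidity, and 9.1 does not say which are tested.

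**The plan's own statement.** Bonferroni level = family level / number of tests.

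- Family level 5%: 0.05/12 = 0.00417, or 0.42%.
- Family level 2.5%: 0.025/12 = 0.00208, or 0.21%.
- Ratio: 0.01/0.00417 = 2.4.
- 1% equals Bonferroni at 5% only for 0.05/0.01 = 5 tests.

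In the usual sense of the word, the statement cannot be reproduced.

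**False-stop chance with no true effect on any endpoint.**

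- 12 independent tests: 1 − 0.99^12 = 11.4%.
- Upper bound under any dependence: 12 × 1% = 12%.
- For comparison, at the Bonferroni level: 1 − (1 − 0.00417)^12 = 4.9%.

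**Leaving out pessary intolerance and harm of intervention**, which are not null comparisons:

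- 10 independent tests: 1 − 0.99^10 = 9.6%.
- Correlated tests: the documents give no correlations, so these are assumed. Simulation used normal test statistics (1,000,000 draws), with correlation 0.3–0.7 among five neonatal tests and 0.2–0.5 among the maternal tests.

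| Neonatal correlation | Maternal correlation | 5 maternal tests | 4 maternal tests (death too rare to reject) |
|---|---|---|---|
| 0.3 | 0.2 | 9.0% | 8.1% |
| 0.5 | 0.2 | 8.5% | 7.7% |
| 0.7 | 0.2 | 7.8% | 7.0% |
| 0.3 | 0.5 | 8.3% | 7.7% |
| 0.5 | 0.5 | 7.8% | 7.2% |
| 0.7 | 0.5 | 7.1% | 6.5% |

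The range is therefore about 6.5–9%. A strong common correlation across all 12 tests would lower the figure further (5.5% at 0.7, 3.1% at 0.9).

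**Pessary intolerance.** Section 4.1.2 defines it as discomfort or pain caused by the pessary, and the table in 9.1 assigns it a between-arm test. A control woman could have it only if she received a pessary, for example as rescue under 5.4. Assume no control cases, and 150 women per arm (300 pregnancies) or 75 (300 children).

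- One-sided Fisher p for x cases against 0 with n per arm is C(n, x)/C(2n, x).
- At n = 150: x = 6 gives 0.015 and x = 7 gives 0.0073. At n = 75: x = 6 gives 0.014 and x = 7 gives 0.0067. Seven cases therefore cross the 1% line.
- P(at least 7 cases) at an assumed 5% rate: 0.63 at n = 150, 0.08 at n = 75.
- At an assumed 10% rate: 0.99 and 0.63.
- With an uncorrected chi-square, six cases are enough, and the 5% figures become 0.77 and 0.17.

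**The negative label.** The interim takes place around birth. The primary evaluation takes place 3 years after the last delivery, and none of the 12 endpoints is the primary outcome. No result of the 12 tests can therefore be a finding on the primary question.

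**The case against.** The strongest reply is that the remark on conservatism opens with the aim of a high safety level. Read whole, it may mean that the trial stops readily for harm, and a threshold looser than Bonferroni does that. This stands: a reader might infer a plain arithmetic slip, but the text supports only ambiguity. An easy stop for harm is also a legitimate choice, and it does not inflate the type I error of the primary test.

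It also stands that 11.4% requires independence. The neonatal endpoints are closely related. Inpatient hospitalisation is itself serious by the definition in 8.2, so two maternal endpoints overlap. Maternal death would need about 6 or 7 cases against none to reject. This is why the figure is given as a range.

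Several stronger readings are tempting, and the documents do not support them:

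- *That the children's 3-year outcomes would be lost after a stop.* No section says that follow-up ceases. Section 4.9 ties the end of the study to the 3-year examination of the surviving children. The fair charge is that follow-up after a stop is not stated.
- *That 9.1 contradicts 9.3.* One is a between-arm test at a fixed interim; the other is a temporary stop after a single maternal death. The triggers differ and both can operate. What is missing is a cross-reference.
- *That maternal tests alone would stop about 5% of trials.* Leaving out intolerance and treating maternal death as too rare to reject leaves four tests. Independence then gives 1 − 0.99^4 = 3.9%, and a correlation of 0.5 about 3.4%.
- *That crossings must go to an external committee.* That would turn a binding rule into an advisory one. It is a separate trade-off and not needed to correct this point.

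**Conclusion.** The concern holds as a defect of description and labelling. The choice to stop readily for harm is not itself an error.

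The count of 12 and the Bonferroni comparison (1% against 0.42%) come directly from the text. The false-stop chance of 11.4% rests on independence and no true effect. The 6.5–9% range rests on the assumed correlations and on leaving out intolerance and harm of intervention.

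A reader might take about 11% as a ceiling for a harmless device. It is not one: a pessary that causes only discomfort could stop the trial with much higher probability. That depends on the intolerance rate, the absence of control cases and the meaning of 300 twins, none of which the documents settle.

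The negative label is unsupported whatever is assumed about correlation, because the primary outcome is not examined at the interim.

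**What to change.** 1. In 9.1, replace the Bonferroni remark with a true statement: 12 one-sided tests at 1% each, deliberately looser than Bonferroni (0.42%) to favour detection of harm. Give a false-stop chance of roughly 6.5–11%, depending on the assumed correlation and on which endpoints are counted (11.4% is all twelve under independence; 9.6% is ten). State that these figures do not cover pessary intolerance or harm of intervention, which are not null comparisons.
2. Replace termination as negative with a stop for the named safety finding. State that enrolled pregnancies and children remain in the already planned 3-year follow-up, and that the primary outcome will be reported with its confidence interval.
3. Cross-reference the interim rule in 9.3 and reconcile the two sections, so that the section on termination criteria is complete.

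The 1% level and its sensitivity to harm stay as they are. The cost is protocol wording, a less favourable stated false-stop figure, and continuation of the planned 3-year questionnaires for families enrolled before a stop.

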Senior Consultant of Department of Obstetrics and Gynecology
- [name], PhD
[contact] – 50
[contact]
Charité – Universitätsmedizin Berlin, [name]
Department of Obstetrics and Gynecology

1.7. Name and address of the medical departments or institutions that are involved in the trial.

Department of Obstetrics and Gynecology international Centres:

- University of Adelaide, Adelaide, Australia
- Medical School of the Aristotle-University of Thessaloniki, Thessaloniki, Greece
- University Hospital of Athens, Athens, Greece
- Vall d'Hebron University Hospital, Barcelona, Spain

Department of Obstetrics and Gynecology in Germany:

- Bürgerhospital Frankfurt/M, [name].
- Kath. Marien Krankenhaus GmbH, [name].
- Vivantes Klinikum im Friedrichshain, [name].
- Universitätsklinikum des Saarlandes, [name].
- Charité – Universitätsmedizin Berlin, [name]
- Universitätsklinikum Frankfurt, [name]

2. Rationale

2.1. Justification of the relevance of the trial.

Preterm birth (PTB) is a major contributing factor to perinatal morbidity and mortality. Prematurity requires intensive medical care for the neonate and is associated with an increased risk of mortality, disability, and developmental disorders later in life.^{1,2}

Women with a twin pregnancy are at increased risk of preterm delivery. In the Netherlands, approximately 50% of women with a multiple pregnancy deliver before 37 weeks' gestation, of whom 9% deliver before 32 weeks.³ Also for the USA the rate of preterm birth was as high as 56.6% in twins and the preterm delivery rate before 32 weeks was 11.3%.⁴

A short cervix (<25 mm) is associated with early and very early preterm birth in twins, and 15% of women with twin gestations have a cervix \leq 25 mm.⁵ This measurement has become the method of choice for screening asymptomatic pregnant women at risk for preterm birth <24 weeks of gestation both in twin and singleton pregnancies.⁶

A cervical pessary to support the cervix in pregnant women with cervical insufficiency was introduced in 1960. A cervical pessary is a silicone ring with a smaller diameter to be fitted around the cervix and a larger diameter to fix the device against the pelvic floor. This effectively rotates the cervix toward the posterior vaginal wall and corrects the cervical angle.⁷

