Women attending the reference hospital due to cervical shortening in twin pregnancies and fulfil the entry criteria (dichorionic twin pregnancy with cervical shortening \leq 25th percentile and do not fulfil the exclusion criteria), the study will be proposed. The patients will be informed of the intended therapeutic effect and possible side effects. If they agree and after obtaining their informed consent, they will be randomised according to the respective gestational week to either usual management (=control group) or cervical pessary placement up to 37 weeks (=pessary group). According to the gestational week and when the cervical shortening is under the 25th percentile the patients will be randomized to the following subgroups: gestational age in weeks 16-20, gestational age in weeks 20-24 and gestational age in weeks 24-28.

Specifically, the 25th centile of cervical length is defined at 32 mm, 30 mm and 28 mm for the 16+0 – 19+6, 20+0 – 23+6 and 24+0 – 28+0 weeks of gestation respectively.

2.3. Name and description of the device under investigation.

The Arabin cervical pessary, which is CE-certified for preventing SPB (CE 0482 / EN ISO 13485: 2012 + AC:2012 annex III of the council directive 93/42 EEC).

See annex I.

2.4. Statement that testing will be performed according to protocol, GCP and applicable legal requirements.

The Clinical Trial will be conducted following the protocol, the GCP, and all legal requirements.

3. Objective

This study aims to investigate the benefit of placing a cervical pessary in comparison to the expectant standard management in dichorionic twin pregnancies with cervical shortening \leq 25 percentile in terms of long-term survival without neurodevelopmental disability of the children.

Hereby, a standardized validated test called 'Ages and Stages 3rd edition' should evaluate the children's neurodevelopment at the age of 3 years. The test can be conducted by the parents and takes approximately 12 minutes. The questionnaires will be provided by the sponsor.

4. Design

4.1. Specific description of primary and secondary variables.

4.1.1. Primary outcome:

- Children`s survival without neurodevelopmental disability at the age of 3.

4.1.2. Secondary outcomes:

[figure not shown]
- Offspring
 - Time to birth
 - Preterm birth before 37 weeks: rate of delivery before 36+6 weeks
 - Preterm birth before 34 weeks: rate of delivery before 33+6 weeks
 - Preterm birth before 32 weeks: rate of delivery before 31+6 weeks

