If a woman with a dichorionic twin pregnancy at a gestational age of 16 weeks up to 28 weeks is diagnosed with a shortened cervix \leq 25 percentile during a preventive examination in pregnancy her vaginal pH-value is checked to preclude a vaginal infection. If her pH-value is $< 4,4$ she will be informed about the ongoing trial. If she is willing to participate and gives her informed consent, the woman will be randomized according to her respective gestational age to either pessary treatment group or expectant management group.

If the pregnant woman is assigned to the pessary group the pessary will be inserted directly. This procedure does not need anaesthesia and it does not need to be done in a surgery room. After the insertion of the pessary the correct fit of the pessary is verified by transvaginal ultrasound and in case it does not fit perfectly, it can easily be adjusted. The pessary will be removed at 37 weeks of gestation, or before if any unexpected event occurs (see 4.6).

After insertion of the pessary the obstetrical management during the pregnancy will be the same in both groups. Further surveillance of the pregnancy will not be influenced by the participation on the study.

4.5. Expected duration of subject's participation.

Study calendar:

Starting recruitment: July 1st, 2018

Finishing recruitment and follow-up: Dec 31st, 2023

Final report: July 2024.

4.6. Completion and interruption criteria of the study or the subjects.

The pessary will be removed at 37+0 weeks of pregnancy. The indications to remove them before this time will be: active bleeding stronger than usual period bleeding, persistent contractions after tocolysis and premature rupture of the membranes after 34 weeks.

After removing the pessary, the obstetrical management will be done as usual and will not be influenced by the study.

4.7. Maintenance of the randomisation codes and test procedures of the trial.

Every participating centre will have its own randomisation list.

We have created a database in a website so it can be accessed worldwide, that every hospital will be able to randomize their patients.

Every center will receive a password and a username in order to access the database for recruitment, randomization and documentation of patient data. Hereby, a personal identification number will be assigned for every patient. Patient names will not appear in the databases.

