The pessary will be inserted during a preventive examination in pregnancy in the examination room. This procedure does not need anaesthesia and it does not need to be done in a surgery room. After the insertion of the pessary the correct fit of the pessary is verified by transvaginal ultrasound and in case it does not fit perfectly, it can easily be adjusted. The pessary will be removed at 37+0 weeks of gestation, or before if any unexpected event occurs (see 4.6).

After insertion of the pessary the obstetrical management during the pregnancy will be the same in both groups. Further surveillance of the pregnancy will not be influenced by the participation on the study.

7. Efficacy assessment

7.1. Specification of efficacy parameters: Primary and secondary endpoints.

This study aims to investigate the benefit of placing a prophylactic cervical pessary in comparison to the usual management in twin pregnancies with cervical shortening ≤ 25 percentile in terms of long-term survival without neurodevelopmental disability of the children.

7.2. Methods and timing to assess records and analyze the efficacy parameters.

The patients will be assessed according to usual management in a twin pregnancy.

	Regular preventive exam	Regular preventive exam	Postnatal evaluation	3 years follow up (corrected age)
Study procedure	study inclusion			
Informed consent	x			

Randomisation	x			
Pessary placement	x			
Pessary removal		x at 37 WoG		
physical exams				
Abdominal US	x	x		
Vaginal US	x Cervical length ≤ 25 percentile			
pH-Value	pH < 4,4			
Neonatal Examination			x	
Ages and stages test				x
Exam at paediatrician				x

8. Assessment of Safety

8.1. Procedures to record and report adverse events.

If a serious and unexpected adverse effect occurs during pessary treatment, it will be notified to the study Sponsor. The Department of Obstetrics and Gynecology of the Sponsor will fill the side effects document to notify it to the *Landesärztekammer Hessen*.

The patient affected by the adverse effect will be followed more intensively during the first days and if nothing else occurs, she will return to the standard control.

8.2. Definitions.

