A medically qualified investigator will assess the relationship of AEs to the study medication.

All SAEs must be reported to the main investigator. He will perform an initial check of the report, request any additional information, and he will notify it to the Ethics Committee. All SAE information will be recorded. It may be appropriate that some SAEs do not require immediate reporting but this must be justified. Justification might be determined, for example, by admission to hospital, or prolongation of hospitalization, where this is to be expected in the underlying disease or condition.

All adverse events (AE) life-threatening or resulting in death will be notified within 24 hours. All AE that are not life-threatening will be notified within 15 days. The rest of AE will be recorded and analyzed at the end of the study.

9. Statistics

9.1. Description of statistical methods.

The primary statistical aim is to compare the primary combined outcome “long-term survival without neuro-developmental disability at 3 years follow up” with a two-sided Cochran-Mantel-Haenszel-Test and a significance level of $\alpha=0.05$. The primary outcome refers to a combined event in any of the twin and will be analysed for all pregnancies with available primary endpoint. The stratified study design is accounted by this stratified test according to the gestation groups.

The main statistical evaluation will be performed at two time points. (1) The complete data set for the secondary endpoints will be available after the last women enrolled in this study has delivered her twins, so the analysis of these outcome parameter will be done right after this event. (2) The primary outcome will be evaluated 3 years after the last woman enrolled in this study has delivered her twins.

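### The primary test does not use baseline cervical length; one pre-specified adjusted analysis may add a little precision if cervical length is prognostic

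*Combined protocol and SAP*

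**What the plan says.** The table of tests in Section 9.1 gives the primary analysis as "Cochran-Mantel-Haenszel-Test, using 3 strata according to WoG". The text of that section adds: "The stratified study design is accounted by this stratified test according to the gestation groups". The unit is the pregnancy, with an event in either twin counting. No other baseline variable enters.

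The schedule in Section 7.2 records vaginal ultrasound at inclusion with the entry "Cervical length ≤ 25 percentile", so the measurement exists for every woman. Section 9.1 uses it only for subgroups: "Further subgroup analyses regarding the cervical length will be performed (e.g. CL 15 to 25mm and below 15mm". Those cut-points are in millimetres, so the measured value is needed in the database anyway.

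Section 2.1 supplies the clinical link in two steps. First: "A short cervix (<25 mm) is associated with early and very early preterm birth in twins". Second, prematurity "is associated with an increased risk of mortality, disability, and developmental disorders later in life". Section 2.2 sets the entry limits by gestation group: "the 25th centile of cervical length is defined at 32 mm, 30 mm and 28 mm".

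Section 9.1 also mentions random-effect regression, but for events per twin and per child, with no covariates named and not as the primary test. On centre, Sections 4.7 and 13 both state "Every participating centre will have its own randomisation list", while Section 9 has no centre term.

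**The concern.** A baseline variable that predicts outcome can be used to narrow the treatment comparison without recruiting anyone. Cervical length is the obvious candidate here. It defines eligibility, it is already measured, and the protocol's own rationale places it on the path to preterm birth and later disability. Only about 62 primary events are expected, a quarter of the women may be lost over three years, and Section 14 reports no funding, so inexpensive precision has some value.

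Pre-specification also matters apart from power. If the arms differ by chance in cervical length, an adjusted analysis chosen after the data are seen would look selective. The plan at present leaves that choice open.

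**Working it through.** **Inputs from the documents.** Two-sided alpha 0.05; pessary event rate 8%; odds ratio 2.29; three equal strata; 250 + 250 evaluable; 25% dropout; 672 recruited (Sections 9.1, 9.2). Ten centres are listed in Section 1.7.

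**Assumed, because the documents are silent.** Odds ratio per SD of shorter cervical length: 1.0, 1.4 or 1.8. Between-centre SD on the logit scale: 0 or 0.5. Allocation in permuted blocks of 4 within centre. Losses at random.

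**1. Reproduce the plan's figure.**
- Control odds = 2.29 × 0.08/0.92 = 0.1991, so the control rate = 0.1991/1.1991 = 16.6%.
- Expected events = 250 × (0.080 + 0.166) = 61.5, about 62.
- Power = Φ{[(n/4)(pC − pP) − c − 1.96√V0]/√V1}, with V0 = (n/4)p̄(1 − p̄), V1 = (n/8)[pP(1 − pP) + pC(1 − pC)], and c = 0.5 with continuity correction or 0 without.
- At n = 500: (n/4)(pC − pP) = 10.76, √V0 = 3.672, √V1 = 3.641.
- Without correction: (10.76 − 7.20)/3.641 = 0.978, power 83.6%. With correction: (10.26 − 7.20)/3.641 = 0.840, power 80.0%.
- Computed explicitly over three strata, the values are 83.4% and 79.8%.
- Dropout: 672 × 0.75 = 504.

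The stated 500 for 80% power is therefore reproduced on the continuity-corrected basis. The design is not short of power without adjustment.

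**2. Approximate gain.** Effective n = n/(1 − R²), where R² is the share of outcome variance explained by a normally distributed covariate.

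| OR per SD | R² | Effective n | Power, no correction (base 83.6%) | Power, corrected (base 80.0%) |
|---|---|---|---|---|
| 1.3 | 0.0074 | 504 | 83.9% | 80.3% |
| 1.5 | 0.0178 | 509 | 84.2% | 80.7% |
| 2.0 | 0.0519 | 527 | 85.5% | 82.2% |

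**3. Simulated gain.** 504 evaluable women; event rates 8% and 16.6%; cervical length drawn from below the 25th centile of a normal distribution and standardised in enrolled women; no centre effect; 16,000 null and 16,000 alternative trials per scenario. The planned CMH test was compared with a likelihood-ratio test that also uses cervical length, each at its own simulated 5% critical value. Simulation standard error is 0.1 to 0.3 points. Two separately coded runs are in brackets. Equivalent women = 504 × (1/r² − 1), where r is the ratio of standard errors of the risk difference.

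| OR per SD, enrolled | Power change, points | Ratio r | Equivalent women |
|---|---|---|---|
| 1.0 | −0.2 (−0.3, −0.5) | 1.001 | −1 |
| 1.4 | +0.4 (+0.4, +0.3) | 0.994 | +6 |
| 1.8 | +1.7 (+1.8, +1.9) | 0.972 | +29 |

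**4. How strong is 1.8?** Below the 25th centile (z = −0.674), λ = 0.3178/0.25 = 1.271. The truncated variance is 1 + 0.674 × 1.271 − 1.271² = 0.24, so the SD is 0.49 of the unselected SD. An odds ratio of 1.8 per enrolled SD is then 1.8^(1/0.49), about 3.3 per unselected SD; 1.4 becomes about 2.0. Because the entry limits fall from 32 to 28 mm across gestation groups, the strata may already carry some of the variation.

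**5. Centre.** Adding centre alone changed power by 0.0 points with no centre effect and by +0.1 to +0.3 points at SD 0.5, although SD 0.5 implies control rates of about 6% to 33% across centres. Its variance was estimated as zero in about 76% of trials with no centre effect and 22% to 24% at SD 0.5.

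**6. Size.** The adjusted test with a random centre intercept had actual size 5.0% to 5.6% (standard error about 0.17 points). A repeat run of the adjusted test gave 4.8% to 5.8%. The planned uncorrected CMH test ran at 4.7% to 5.4% in the main simulation. This is why power is compared at equal size: at the nominal level, part of any apparent gain would be a difference in size.

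**The case against.** The strongest objection is that no defect exists. The CMH test on gestation groups is valid, and it matches both the stratified design and the basis of the sample size. Preferring a regression model may be no more than taste. That stands as far as severity goes: this is an optional improvement and not an error.

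It is also fair to say that the gain is conditional. Section 2.1 links a cervix below 25 mm to preterm birth, and prematurity to later harm. It gives no gradient for the 3-year outcome among women already selected for a short cervix. Nearly all of the benefit shown comes from the 1.8 case.

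Four stronger readings are tempting, and the documents do not support them:
- A reader might infer that the trial is underpowered or the primary test invalid without adjustment. The plan's own figure reproduces, and leaving out a prognostic covariate does not affect the size of the test.
- A reader might infer that adjustment is certain to help. At an odds ratio of 1.0 it costs a few tenths of a point.
- A reader might infer that separate randomisation lists make the missing centre term a source of lost power. The gain from centre is within or close to simulation error. Any slight conservatism from ignoring centre depends on balanced allocation within centre, and the protocol mentions lists but no block scheme.
- A reader might infer that cervical length is ignored altogether. It sets eligibility and is planned for subgroups; only the primary test leaves it out.

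**Conclusion.** The point holds as a minor, conditional gain in efficiency. If cervical length is moderately prognostic in enrolled women (odds ratio 1.4 per SD), adjustment is worth about 0.4 points of power, or the precision of about 6 more women. If it is strongly prognostic (1.8), it is worth 1.7 to 1.9 points, or about 29 women. If it is not prognostic, the result is no gain or a slight loss. The power figures apply only if the adjusted model is the primary test; otherwise the benefit is confined to the precision of the reported estimate. All of this rests on assumed prognostic strength, losses at random and the event rates in Section 9.2. The small end of the range is the more credible, given the narrow span of cervical length at entry.

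**What to change.** In Section 9.1, keep the stratified CMH test as the primary test. Add one pregnancy-level logistic regression of the primary outcome on arm, gestation group and continuous baseline cervical length, and name it as the adjusted analysis. Report the adjusted odds ratio and a standardised risk difference, each with a 95% confidence interval by a stated method (for example the delta method or the bootstrap).

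If the sponsor prefers the adjusted model as primary in order to obtain the power gain, that choice must be written down before any outcome data are seen. In this plan that means before the interim safety analysis, which already examines deaths and neonatal morbidity.

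A random centre intercept may be listed as an optional sensitivity analysis because lists are kept by centre. Centre should not be added as further CMH strata: 10 centres × 3 gestation groups gives 30 cells, or about 62/30 ≈ 2 events per cell.

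The cost is a few sentences and slightly more analysis work. No new data are needed, and R is already named in the plan. The downsides to accept are:
- the adjusted odds ratio is conditional and not directly comparable with 2.29, hence the risk difference alongside;
- with about 62 events the likelihood-ratio test may run slightly above nominal size, up to about 5.8% in simulation;
- if the model were made primary and cervical length proved not prognostic, a few tenths of a point of power would be lost.
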